1.0 TRIAL SUMMARY

[figure not shown]
Protocol Number/Title	CASE 6316 A Phase II Study of the Addition of Pembrolizumab to Postoperative Radiotherapy in Resected High Risk Cutaneous Squamous Cell Cancer of the Head and Neck
Study Phase	II
Brief Background/Rationale	While outcomes in resected cutaneous squamous carcinomas are typically very favorable, a subset of high risk resected cancers in the head and neck have a more aggressive disease course despite the routine use of adjuvant radiotherapy. This trial is a treatment intensification protocol which seeks to establish the safety and efficacy of concurrent and adjuvant Pembrolizumab in combination with radiation in the adjuvant treatment of high risk cutaneous squamous cell cancer of the head and neck.
Primary Objective	To assess safety (% of DLTs) and estimate 1-year PFS of postoperative RT + concurrent and adjuvant Pembrolizumab in high risk resected cSCC-HN.
Secondary Objective(s)	Patterns of Failure
Correlative Objective(s)	
 1) To evaluate the relationship of baseline PD-L1 expression by tumor and tumor-infiltrating lymphocytes (TILs) to preliminary efficacy. 2) To phenotype tumor infiltrating lymphocytes and peripheral blood lymphocytes (PBLs), and investigate tumor suppressor populations including Tregs, MDSCs and CD8 suppressor cells and assess ex vivo for effector function by cytokine production and cytotoxicity assays as well as suppressor function in assays with autologous PBLs. 3) To evaluate the tumor microenvironment (TME), and immune markers at the invasive margin of the tumor, including CD8, PD-1, PD-L1, TIM-3, galectin-9 or HMGB-1, BTLA and HVEM, as well as Lag-3, CTLA-4 and others. 4) To evaluate the genomic and/or transcriptomic profile of these tumors using RNA-seq /Whole Transcriptome Shotgun Sequencing
Sample Size	37 participants Age >18, Male and females eligible
Disease sites/Conditions	Skin cancer of the head and neck (squamous)
Interventions	IMRT 60-66Gy over 6 weeks
	Pembrolizumab every 3 weeks for 16 weeks (6 doses)

2.0 TRIAL DESIGN

2.1 Trial Design

- This is a phase II trial evaluating the addition of concurrent and adjuvant fixed-dose pembrolizumab in combination with standard IMRT, in order to establish safety and estimate efficacy of this regimen to be tested in a subsequent randomized registration trial. Thirty seven patients will be enrolled.
- The primary safety endpoint will be proportion of DLTs. The primary efficacy endpoint will be 1-year PFS. The primary signal to move forward with a subsequent confirmatory randomized study will be a $\leq 24\%$ overall DLT rate and a favorable 1yr PFS estimate compared to historical controls.

2.2 Trial Diagram

3.0 OBJECTIVE(S) & HYPOTHESIS(ES)

3.1 Primary Objective(s) & Hypothesis(es)

(1) **Objective:** To assess safety and estimate 1-year PFS of postoperative RT + concurrent and adjuvant Pembrolizumab in high risk resected cSCC-HN.

Hypothesis: The addition of concurrent and adjuvant Pembrolizumab to postoperative RT in high risk cutaneous SCC will be safe and yield favorable 1yr PFS results.

3.2 Secondary Objective(s) & Hypothesis(es)

(1) **Objective:**

- 5) To evaluate the relationship of baseline PD-L1 expression by tumor and tumor-infiltrating lymphocytes (TILs) to preliminary efficacy .
- 6) To phenotype tumor infiltrating lymphocytes and peripheral blood lymphocytes (PBLs), and investigate tumor suppressor populations including Tregs, MDSCs and CD8 suppressor

cells and assess ex vivo for effector function by cytokine production and cytotoxicity assays as well as suppressor function in assays with autologous PBLs.

- 7) For those participants for whom tumor tissue is available, we will evaluate the tumor microenvironment (TME), and immune markers at the invasive margin of the tumor, including CD8, PD-1, PD-L1, TIM-3, galectin-9 or HMGB-1, BTLA and HVEM, as well as Lag-3, CTLA-4 and others.
- 8) If sufficient tumor is available, we will also evaluate the genomic and/or transcriptomic profile of a subset of tumors using RNA-seq /Whole Transcriptome Shotgun Sequencing

Hypotheses:

- 1) Baseline PD-L1 expression will not be associated with 1yr PFS.
- 2) Peripheral immune profiles on PBMC will dynamically change from baseline through treatment and after completion of therapy and correlate with 1yr PFS.
- 3) Changes in the TME at the marginal edge of the tumor will correlate with 1yr PFS and be marker dependent.
- 4) Baseline genomic/proteomic tumor profiles will correlate with 1yr PFS

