4.2.3.3 Rationale for Correlative Endpoints/Biomarker Research

Central hypothesis: Cutaneous squamous cell carcinoma (CSCC) is responsive to combination of PD-1 inhibition and radiation therapy.

To test our hypothesis correlatively we propose the following aims:

Aim 1. To correlate baseline PD-1 expression in the tumor with disease related outcomes.

Rationale: It is unknown whether patients with tumors that express higher levels of PD-1 preferentially respond compared to those that do not. As such, this will be systematically evaluated on all patients.

Research Plan: FFPE tissue blocks will be collected from patients and slides will be cut for subsequent biomarker staining. Analysis of PD-L1 expression will be performed by immunohistochemical staining using the Merck assay. Either complete circumferential or partial linear plasma membrane staining will constitute positive PD-L1 staining. A cut-off of $\geq 5\%$ tumor cell membrane staining will be reported as positive.

Aim 2. To define response to radiation/PD-1 inhibition based on tumor microenvironment and peripheral blood alterations in patients with CSCC.

Rationale: Many solid tumors do respond to checkpoint inhibitors. Little is known in regards to CSCC patients who will or will not respond to the proposed treatment regimen of post-operative radiation and anti-PD-1 therapy.

Research Plan: Prospectively we will stratify study patients into two groups: those that do, or do not respond to the proposed therapy based on historical published data from our institution. The following are the proposed assays for evaluation.

A. Peripheral Blood Lymphocytes

Flow cytometry: Peripheral blood samples drawn from patients pretreatment and at specified times post treatment will be isolated by centrifugation. Surface biomarker expression will be assessed by FACS similar to the analysis of tumor-resident lymphocytes. Staining will evaluate CD3, CD4, CD8 expression as well as cytotoxic markers (perforin, FasL, Granzyme A&B, markers of dysfunction/exhaustion (PD-1, TIM-3, Lag-3), and markers characteristic of regulatory cells (Foxp3, CD25, GITR, CD27, CD28) and markers for myeloid derived suppressor cells. Finally, we will assess TCR clonal diversity using PCR methods.

B. Tissue

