8.0 STATISTICAL ANALYSIS PLAN

8.1 Study Design

This is a phase II trial evaluating the addition of concurrent and adjuvant fixed-dose pembrolizumab in combination with standard IMRT, in order to establish safety and estimate efficacy of this regimen to be tested in a subsequent randomized registration trial. At the conclusion of the study, the primary safety endpoint will be proportion of DLT. The primary efficacy endpoint will be 1-year PFS. Progression-free survival (PFS) will be calculated from treatment initiation to disease progression or death from any cause or last follow up.

8.2 Justification of Design and Sample Size:

The target sample size will be 34 patients. Assuming a <10% drop out or ineligibility rate, 37 patients will be enrolled to ensure 34 evaluable patients (all evaluable patients will be analyzed). The sample size was generated based on the primary safety endpoint. DLT $\leq 20\%$ is acceptable and $\geq 40\%$ is unacceptable. If 11 or more of 34 patients experience DLT, this regimen will be considered too toxic. The significance level and power of this design are 6% and 86%, respectively. If 8 or fewer patients experience DLTs, the regimen will be deemed safe to proceed for further study. If 9 or 10 patients experience DLTs, the PI will examine the type, reversibility and duration of DLTs and a careful decision will be made whether to pursue this regimen further in this adjuvant population.

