8.3 Statistical Analysis Plan

DLT will be estimated using an exact 95% confidence interval. If 11 or more patients experience DLT the regimen will be considered too toxic. One-year PFS will be estimated using the Kaplan-Meier method and a 95% confidence interval constructed using Greenwood's method. One year PFS outcomes will be assessed overall and also separately for immunocompetent patients vs. immunosuppressed patients (e.g. CLL). These outcomes will be compared to our historical dataset for both subsets respectively. Adverse events will be tabulated by category and grade. The rates of

adverse events will be estimated using an exact 95% confidence. The relationship between 1yr PFS and baseline PD-L1 expression will be assessed using logistic regression. Immunoprofiles in peripheral blood in serial samples will be tested using random effects ANOVA. Bioinformatic analysis will be applied to all genomic and transcriptomic data.

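### Hypothesis 1 predicts no association between PD-L1 and 1-year PFS, but a logistic regression in about 34 patients cannot tell no association from one that was not detected

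*Combined protocol and SAP*

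**What the plan says.** Section 3.2 lists four hypotheses. Three predict a correlation with 1-year PFS. The first predicts none: "Baseline PD-L1 expression will not be associated with 1yr PFS". The matching objective in the same section is neutral and speaks only of evaluating the relationship. The trial summary (section 1.0) lists the item as correlative, while section 3.2 lists it as secondary.

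Section 8.3 gives the analysis in one sentence: "The relationship between 1yr PFS and baseline PD-L1 expression will be assessed using logistic regression". It states no test, significance level, PD-L1 coding, margin or confidence interval for this analysis, although it names 95% confidence intervals for DLT, 1-year PFS and adverse events.

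On size, section 8.2 says "The target sample size will be 34 patients" and "The sample size was generated based on the primary safety endpoint". Section 4.2.3.3 sets a 5% staining cut-off for PD-L1 positivity, which suggests a binary predictor, and says of the related marker: "It is unknown whether patients with tumors that express higher levels of PD-1 preferentially respond compared to those that do not".

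**The concern.** A hypothesis of no association is not supported by failing to reject it. Support requires an estimate precise enough to exclude associations that would matter. Here a predicted null is paired with an ordinary test of association, in a sample chosen for another endpoint, and with no rule for interpretation. The most obvious way to use the result would be to take a non-significant coefficient as agreement with the prediction. If that outcome is likely even when PD-L1 matters, it carries little information.

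What is at stake is the wording of one correlative result: a report that PD-L1 is unrelated to 1-year PFS when the data are compatible with a several-fold difference in odds either way.

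**Working it through.** **Inputs from the documents.** 34 evaluable patients (37 enrolled) and the DLT rule, section 8.2; logistic regression, section 8.3; the 5% PD-L1 cut-off, section 4.2.3.3.

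**Assumed, because the documents give no figure for this analysis.** PD-L1 positive in 30% or 50% (splits of 10/24 and 17/17); overall 1-year event rate of 20%, 30% or 40%; two-sided 5%. The odds ratio (OR) is for progression or death by one year, PD-L1-positive against PD-L1-negative.

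**Step 1: the plan's own figure.** The rule is: "If 11 or more of 34 patients experience DLT, this regimen will be considered too toxic". With X binomial (n = 34), P(X ≥ 11) is 0.062 at a 20% DLT rate and 0.862 at 40%. These match the stated 6% and 86%. Allowing for 8% loss, 34 / 0.92 = 36.96, which rounds up to 37. The sample size is sound for its own purpose. No power or precision figure exists for PD-L1.

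**Step 2: chance of a non-significant result.** For each scenario, solve for event probabilities p1 (positive) and p0 (negative) such that

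- [p1/(1 − p1)] / [p0/(1 − p0)] = OR, and
- (n1·p1 + n0·p0)/34 = overall event rate.

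Then sum the binomial probabilities of every 2×2 table whose likelihood-ratio chi-square is 3.84 or less. Example: with a 17/17 split, a 30% event rate and OR 3, p0 = 0.189 and p1 = 0.411 (odds 0.233 and 0.698; mean 0.30). The result is non-significant with probability 68%.

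| True OR | Non-significant, likelihood-ratio test |
|---|---|
| 1 | 93-95% |
| 2 | 82-86% |
| 3 | 64-75% |
| 1/3 | 64-79% |
| 4 | 49-64% |
| 5 | 38-55% |
| 10 (17/17 split) | 12-32% |

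Direction matters in the 10/24 split, so the OR 3 range should not be read as covering OR 1/3. The Wald test gives 83-96% at OR 2 and 66-92% at OR 3, but its upper ends come partly from tables with an empty cell, where the statistic is undefined and was counted as non-significant. The likelihood-ratio figures are the fairer ones.

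A second set of assumptions (30-70% positive, 1-year PFS of 50-80% in PD-L1-negative patients) gives likelihood-ratio power of 11-18% at OR 2 and 16-35% at OR 3, so 65-84% non-significant at OR 3.

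If PD-L1 were modelled as continuous, approximate power would be 37-51% at OR 2 per standard deviation and 73-88% at OR 3 per standard deviation (PFS 60-80%).

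**Step 3: precision if the data agreed perfectly with the hypothesis.** Take an observed OR of 1.0 in a 17/17 split, with events shared equally. The standard error of log OR is the square root of the summed reciprocals of the four cells.

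- 7 events (3.5 per group, notional): √(2/3.5 + 2/13.5) = 0.848; exp(±1.96 × 0.848) = 0.19 to 5.3.
- 14 events: √(2/7 + 2/10) = 0.697; exp(±1.96 × 0.697) = 0.26 to 3.9.

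**Step 4: the best 34 patients can do.** The standard error is smallest when the four cells are nearly equal (8, 8, 9, 9): √(2/8 + 2/9) = 0.687, and exp(1.96 × 0.687) = 3.85. No table of this size without an empty cell gives a 95% interval narrower than 3.85-fold either side of the estimate. An illustrative equivalence range of 0.5-2.0 allows only 2-fold either side of 1, so it could never be met. Meeting it with 80% power at a true OR of 1 would take about 298 to 446 patients (one-sided 5% tests, equal groups, 1-year PFS 60-80%).

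**The case against.** Four objections have force.

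**The documents set no decision rule.** A reader might infer that p > 0.05 will be declared confirmation. Nothing says so. Logistic regression also yields an odds ratio, and the objective in section 3.2 is neutral. This stands: the risk comes from the absence of any other criterion, not from a stated intention.

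**A null result is not certain.** A reader might infer that non-significance is the likely outcome whatever the truth. That goes too far. At OR 5 the chance is 38-55%, at OR 10 with balanced groups it is 12-32%, and a strong continuous effect would probably be found.

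**The next trial does not depend on it.** A reader might infer that a null finding would lead to an unselected randomized trial. The go-forward signal in section 2.1 uses the DLT rate and 1-year PFS against historical controls. PD-L1 plays no part, and no section ties later eligibility to this analysis.

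**Small biomarker analyses are normal in phase II.** That is true, and lack of power is not the complaint. The complaint is a predicted null that such an analysis cannot support.

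The sentence in section 4.2.3.3 calling the question unknown is weak support at most. It refers to PD-1, although the research plan beneath it measures PD-L1, and an open question does not forbid a prediction.

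**Conclusion.** The point holds as a minor one. With binary PD-L1 and about 34 patients, the plan cannot support hypothesis 1 and gives no criterion separating no association from non-detection. Under the stated assumptions, an association of OR 2 would be missed in 82-86% of trials and OR 3 in 64-75% (64-79% for OR 1/3). At OR 4 the chance of detection is at best about even. Only an OR of about 5 or more, or a strong effect with continuous PD-L1, could be more likely than not to be detected.

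The percentages rest on assumed prevalence, event rate, coding and significance level. The limit on precision in step 4 rests only on 34 patients and a binary marker. Missing PD-L1 results, or patients censored before one year whose handling in the logistic model is not described, would reduce the usable number further. The DLT rule is unaffected. The documents support neither the view that non-significance is bound to occur nor the view that the randomized trial's population hangs on this result.

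**What to change.** In section 3.2, replace hypothesis 1 with: *The association between baseline PD-L1 and 1-year PFS will be estimated (exploratory).*

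In section 8.3, add that the odds ratio will be reported with its 95% confidence interval, and that p > 0.05 alone will not be taken as evidence of no association. In the same edit, state how PD-L1 is coded and how patients censored before one year are handled.

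An equivalence margin is not worth adding. With 34 patients, a range such as 0.5-2.0 would always return an inconclusive result.

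The cost is a few sentences and no new data. The trial gives up a claim that its design cannot support.

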4.0 BACKGROUND & RATIONALE

4.1 Background

Refer to the Investigator's Brochure (IB)/approved labeling for detailed background information on MK-3475.

4.1.1 Pharmaceutical and Therapeutic Background

The importance of intact immune surveillance in controlling outgrowth of neoplastic transformation has been known for decades. Accumulating evidence shows a correlation between tumor-infiltrating lymphocytes (TILs) in cancer tissue and favorable prognosis in various malignancies. In particular, the presence of CD8+ T-cells and the ratio of CD8+ effector T-cells / FoxP3+ regulatory T-cells seems to correlate with improved prognosis and long-term survival in many solid tumors.

The PD-1 receptor-ligand interaction is a major pathway hijacked by tumors to suppress immune control. The normal function of PD-1, expressed on the cell surface of activated T-cells under healthy conditions, is to down-modulate unwanted or excessive immune responses, including autoimmune reactions. PD-1 (encoded by the gene *Pdcd1*) is an Ig superfamily member related to CD28 and CTLA-4 which has been shown to negatively regulate antigen receptor signaling upon engagement of its ligands (PD-L1 and/or PD-L2). The structure of murine PD-1 has been resolved.

PD-1 and family members are type I transmembrane glycoproteins containing an Ig Variable-type (V-type) domain responsible for ligand binding and a cytoplasmic tail which is responsible for the binding of signaling molecules. The cytoplasmic tail of PD-1 contains 2 tyrosine-based signaling motifs, an immunoreceptor tyrosine-based inhibition motif (ITIM) and an immunoreceptor tyrosine-based switch motif (ITSM). Following T-cell stimulation, PD-1 recruits the tyrosine phosphatases SHP-1 and SHP-2 to the ITSM motif within its cytoplasmic tail, leading to the dephosphorylation of effector molecules such as CD3 ζ , PKC θ and ZAP70 which are involved in the CD3 T-cell signaling cascade. The mechanism by which PD-1 down modulates T-cell responses is similar to, but distinct from that of CTLA-4 as both molecules regulate an overlapping set of signaling proteins. PD-1 was shown to be expressed on activated lymphocytes including peripheral CD4+ and CD8+ T-cells, B-cells, T regs and Natural Killer cells. Expression has also been shown during thymic development on CD4-CD8- (double negative) T-cells as well as subsets of macrophages and dendritic cells. The ligands for PD-1 (PD-L1 and PD-L2) are constitutively expressed or can be induced in a variety of cell types, including non-hematopoietic tissues as well as in various tumors. Both ligands are type I transmembrane receptors containing both IgV- and IgC-like domains in the extracellular region and contain short cytoplasmic regions with no known signaling motifs. Binding of either PD-1 ligand to PD-1 inhibits T-cell activation triggered through the T-cell receptor. PD-L1 is expressed at low levels on various non-hematopoietic tissues, most notably on vascular endothelium, whereas PD-L2 protein is only detectably expressed on antigen-presenting cells found in lymphoid tissue or chronic inflammatory environments. PD-L2 is thought to control immune T-cell activation in lymphoid organs, whereas PD-L1 serves to dampen unwarranted T-cell function in peripheral tissues. Although healthy organs express little (if any) PD-L1, a variety of cancers were demonstrated to express abundant levels of this T-cell inhibitor. PD-1 has been suggested to regulate tumor-specific T-cell expansion in subjects with melanoma (MEL). This suggests that the PD-1/PD-L1 pathway plays a critical role in tumor immune evasion and should be considered as an attractive target for therapeutic intervention.

Pembrolizumab is a potent and highly selective humanized monoclonal antibody (mAb) of the IgG4/kappa isotype designed to directly block the interaction between PD-1 and its ligands, PD-L1 and PD-L2. KeytrudaTM (pembrolizumab) has recently been approved in the United States for the treatment of patients with unresectable or metastatic melanoma and disease progression following ipilimumab and, if BRAF V600 mutation positive, a BRAF inhibitor.

4.1.2 Preclinical and Clinical Trial Data

Refer to the Investigator's Brochure for Preclinical and Clinical data.

4.2 Rationale

4.2.1 Rationale for the Trial and Selected Subject Population

Disease Background:

Cutaneous squamous cell cancer (cSCC) is the second most common cancer in the U.S. with an estimated incidence of over 700,000 people annually.¹ While most are highly curable with surgery alone, there is a well-recognized subset of patients who demonstrate an aggressive clinical phenotype marked by locoregional recurrence and/or distant metastatic spread. These patients are overwhelmingly comprised of cSCC of the head and neck (cSCC-HN), and frequently demonstrate high risk features including large T3/4 tumors, nodal involvement, lymphovascular space invasion, perineural invasion, and multiply recurrent disease.² In a recent population based study, as many as 5,600 patients were estimated to develop nodal metastases and up to 8,700 deaths were attributable to cSCC.¹ Postoperative radiotherapy has been shown in a number of studies to reduce locoregional recurrence and in some studies improve overall survival in this disease.³⁻⁶ However, there are currently no randomized data supporting the use of systemic therapy concurrently and/or adjuvantly to RT, and significant failure rates, both locoregionally and distantly, underscore the limited treatment options for these patients and the need for intensification strategies in addition to RT.

While radiation is typically a highly effective treatment for both cutaneous and mucosal SCC of the head and neck, a mechanism of radioresistance that is becoming increasingly clarified is the tumor microenvironment altering and inhibiting the innate immune response of the host. As a result of recruitment of inhibitory immune cells (e.g. Tregs; activated macrophages), T-cell activation is suppressed and treatment resistance emerges. PD-1 is expressed by multiple immune cells (e.g. cytotoxic T cells, NK cells, dendritic cells) and when coupled with its ligands PD-L1 and PD-L2, the complex promotes "immune escape" in a number of cancers.^{7, 7, 13, 14} In mucosal head and neck cancer specifically, PD-L1 expression is common, and has been demonstrably linked to the immune-privileged, invasive front of HPV + SCC.^{8,9} A recently completed Phase Ib/II study in mucosal head and neck cancer supported this hypothesis as Pembrolizumab, a high-affinity IgG4 mAb which blocks the interaction of PD-1 with both PD-L1 and PD-L2, produced impressive response rates (20% by RECIST criteria) in heavily pretreated recurrent/metastatic patients.¹⁰

Cutaneous SCC of the head and neck shares many parallels with mucosal SCC as they are both considered to be more prevalent in "immune-weakened" states. While mucosal disease demonstrates

defective antigen presenting cells (APC), and quantitative and qualitative T lymphocyte deficiencies, skin cancer is a disease of aging as older, less robust immune systems become less effective at preventing sun damaged mutated skin cells from cancerization.^{11,12} There is early emerging work implicating PD-1 in particular in cutaneous SCC pathways. A recent study demonstrated that immune neutralization of PD-1⁺ cells resulted in decreased papilloma incidence in mice which was associated with CD4⁺ and CD8⁺ T cell infiltrates, as well as increased interferon- γ and decreased transforming growth factor- β production within tumors, supporting the role of PD-1 blockade in SCCS.¹³ Another study associates a higher incidence of seropositivity to particular strains of papillomavirus in organ transplant patients as a potential mechanism for the increased incidence in cSCC in these patients, highlighting an important potential overlap between cSCC-HN and mucosal head and neck cancer, known to be frequently HPV induced.¹⁴

Radiotherapy induces immune responses by releasing tumor antigen, recruiting chemokines and making cells more vulnerable to T-cell killing.¹⁵ PD-L1 upregulation following RT in the tumor microenvironment has been recently demonstrated, and inhibiting its activity using anti-PD-L1 treatment enhanced the effectiveness of RT via a cytotoxic T-cell dependent mechanism.¹⁶ A recent landmark study in melanoma analyzed samples from 46 patients treated with Pembrolizumab and found that tumor regression after therapeutic PD-1 blockade required pre-existing CD8(+) T cells that are negatively regulated by PD-1/PD-L1-mediated adaptive immune resistance.¹⁷ This emerging picture of the importance of the immune response in general, and the PD-1 pathway in particular, being highly associated with carcinogenesis and response to RT provides a sound basis to pursue PD-1 blockade in high risk cSCC-HN.

